Secondary objective (d) will be evaluated using mixed effect models allowing for random variation in symptoms of bipolar disorder and depression at baseline. The null hypothesis for this objective will be that change in symptoms and suicidal ideation in the lithium group is similar to that of the placebo group. The alternative hypothesis is that there is a difference in change across treatment groups over time.

Secondary objective (e) will be evaluated by regression analysis method comparing regression coefficients for treatment effect in the models with and without the mediator (Sobel, 1982), as well as by bootstrapping methods, (MacKinnon et al., 2002; Preacher & Hayes, 2008; Tein & MacKinnon, 2003).

Tertiary Data Analysis Plan

These exploratory objectives (explained further in Section XIV) are to analyze electronically available data over the extended follow up period to:

- (a) describe pattern of Lithium use following active participation in the study participants,
- (b) evaluate suicide reattempt and all cause mortality over a longer follow up period, both for the study population and patients who were evaluated for enrollment under HIPAA waiver (“pre-screen” population), and
- (c) evaluate all cause mortality over a longer follow up period.

Tertiary objective (a) will be evaluated by descriptive analysis on duration of lithium use, and by regression modeling to determine factors associated with any lithium use within one month following active study participation.

Tertiary objectives (b) and (c) will be evaluated using time to event survival analysis and Cox regression modeling to determine correlates of suicide reattempts and all cause mortality in the study population.

Data Repository

The Boston CSP Coordinating Center will create a data repository under the Boston IRB oversight for research purposes. Data will be housed at the Boston Cooperative Studies Program Coordinating Center and will be made available to appropriately credentialed researchers conducting studies related to suicide, lithium, or other health questions, in accordance with the Repository Protocol and relevant SOPs.

VIII. POTENTIAL PITFALLS OF THE PROPOSED DESIGN AND ALTERNATIVE DESIGN CONSIDERATIONS

Potential pitfalls of the trial include the threats to internal and external validity inherent in any clinical trial and those of particular concern to this study question.

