Psychiatric Diagnosis	Mini-International Neuropsychiatric Interview (Sheehan et al., 1998)	MINI	Structured interview to elicit psychiatric symptoms and determine diagnoses	Interview	Variable	Eligibility	20
	PTSD Checklist (modified to allow DSM-IV-TR and DSM-5 diagnoses); Blanchard et al., 1996)	PCL	Self-rating scale to be administered as a structured interview	Self or Interview	22	Potential covariate for exploratory analyses	6
	Substance use disorders module from Structured Clinical Interview for DSM-IV-TR Axis I Disorders (First et al., 2002)	SCID SUD	Supplementary questions related to substance use diagnoses	Interview	Variable	Eligibility	10
Cognition and Decision-Making Capacity	Orientation Memory Concentration Test (Katzman et al., 1983)	OMC	Cognitive screening instrument	Interview	6	Eligibility	6
	The Jeste Decision-Making Capacity Assessment – University of California, San Diego Brief Assessment of Capacity to Consent (UBACC)	UBACC	Evaluation of decision-making capacity	Interview	Variable	Eligibility	5

[name]: CSP#590 Lithium for the Prevention of Recurrent Suicide Attempts

Mental Health Symptoms	Patient Health Questionnaire-9 (Kroenke et al., 2001)	PHQ-9	Symptoms of depression	Self or Interview	10	Secondary Outcome	7.5
	Internal State Scale (Bauer et al., 2000)	ISS	Symptoms of bipolar disorder	Self or Interview	15	Secondary Outcome	7.5
	Alcohol Use Disorders Identification Test-C (Bradley et al., 2007)	Audit C	Quantity-frequency data on alcohol use	Interview	3	Secondary Outcome	3
Moderators	Buss-Perry Aggression Scale (Buss & Perry, 1992)	Buss Perry	Aggression as a trait	Self	29	Secondary Outcome	10
	Barratt Impulsiveness Scale (Patton et al., 1995)	Barratt	Impulsivity as a trait	Self	30	Secondary Outcome	10
Lithium side effects	Lithium side effects checklist		Systematic review of possible lithium side effects	Interview	8	Monitoring	5
Use of VA and non-VA health and mental health services (Sirey et al., 2005)	Self-report log based on the Cornell Services Index (Sirey et al., 2005)		Use of health and mental health services to include patient's report of reasons for hospitalization or emergency department visits	Log maintained by subject and reviewed by research staff at each visit	Variable	Monitoring	5 minutes for review

Table 2: Comparison of select prior studies of lithium with CSP590

	Cipriani (2005)	Guzzetta (2007)	Goodwin (2003)	Lauterbach (2008)	Oquendo (2011)	Proposed CSP590

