5.1. Secondary Objective

This trial has 5 secondary objects, which are described below. Analyses for these objectives are exploratory in nature and as such, they are not statistically powered for formal hypothesis testing. These objectives are to:

- 1) explore the effectiveness of lithium augmentation of enhanced suicide prevention management in preventing separately:
 - a. all-cause mortality
 - b. impulsive suicide reattempts
 - c. non-impulsive suicide reattempt
 - d. non-suicidal self-directed violence
- 2) explore heterogeneity of response to treatment subgroups including:
 - a. categories of age, race/ethnicity, and gender
 - b. diagnosis of depression vs. bipolar disorder
 - c. impulsive index attempt vs. non-impulsive index attempt
 - d. substance use vs. absence of substance use
 - e. individuals with and without trait impulsivity
 - f. individuals with and without trait aggression
 - g. subjects who have vs. have not received evidence based psychotherapies
- 3) explore the effect of lithium augmentation of enhanced suicide prevention management on total occurrence of all event types and cumulative occurrence of individual event type as follows:
 - a. all suicide attempts
 - b. all hospitalizations for prevention of suicide attempts
 - c. all self-directed violence
 - d. all emergency department visits

- 4) explore longitudinally the effect of lithium augmentation of enhanced suicide prevention management on symptoms of bipolar disorder and depression and suicidal ideation
- 5) explore mediators of the effect of lithium augmentation on prevention of suicide reattempt, specifically improved control of symptoms and lithium plasma levels

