5.2. Secondary Endpoints

There are multiple secondary endpoints being considered for the study where endpoint events for secondary objectives #1, 2, and 5 will be assessed as time to event outcomes, endpoint events for secondary objective # 3 will be assessed as count data, and endpoint events for Secondary Objective #4 will be evaluated as a binary outcome.

For Secondary Objective #1, Time from randomization to death from any cause will be analyzed. Additionally, self-directed violence as described in section 4.2 will be classified further as either impulsive or non-impulsive attempt based on Beck Suicide Intent Scale, (Question#15 on CRF-Form S8), and will be analyzed separately. Lastly, non-suicidal self-directed violence behavior defined as the primary endpoint without the death from suicide will be considered as a separate outcome.

For Secondary Objective #2 which evaluates efficacy in different subgroups, the primary endpoint as described in section 4.2 will be analyzed.

The endpoint for Secondary Objective #3 considers all components of self-directed violence as described in section 4.2. Therefore, a combined total of all episodes of all components of the primary outcome will be an endpoint, and total counts of each component, in addition to all emergency department visits will be separate endpoints.

For Secondary Objective #4, dependent variables being considered longitudinally include (1) presence or absence of symptoms, and (2) presence or absence of suicidal ideation. Presence or absence of symptoms will be derived by the Internal State Scale (CRF-Form B8), and presence or absence of suicidal ideation will be derived from the Columbia Follow Up Questionnaire (CRF-Form B6).

Lastly, for Secondary Objective #5, the endpoint event will be the same as the primary endpoint described in section 4.2.

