5.3. Statistical Methods for Secondary Analyses

Secondary objective#1 will use a time to event, survival analysis to determine whether there is a treatment difference in event rates for each of the defined endpoints. The null hypothesis for each endpoint is that the two treatment groups do not differ in their hazard

rates. The alternative hypothesis is that the intervention group on lithium has a lower hazard rate than the placebo group. As with the primary analysis, log-rank test and Cox proportional hazards models will be used.

For secondary objective#2, the null hypothesis for each of the factors is that treatment effect does not differ over levels of the factor. The alternative hypothesis is that there is differential treatment effect over levels of the factor. Effect modification will be evaluated through regression methods. Cox proportional hazards regression model will include the treatment term, a term for the target factor, and the interaction term of the two. If the null hypothesis is rejected at $p=0.05$ level, i.e., the interaction term in the model is statistically significant, separate regression models will be refitted for each level of the factor. A forest plot will be used to display the results.

For secondary objective#3, the null hypothesis is that total event rates do not differ by treatment assignment, and the alternative hypothesis is that there is a difference in total event rates across treatment groups. We will use Generalize Linear Models (glm), namely Poisson regression, to model cumulative total of endpoint events with an offset for follow up time.

For secondary objective#4, the null hypothesis is that change in symptoms and suicidal ideation in the lithium group is similar to that of the placebo group. The alternative hypothesis is that there is a difference in change across treatment groups over time. We will use Generalize Linear Models (glm), namely Logistic regression, to model presence or absence of symptoms and suicidal ideation at each follow up visit, while allowing for random effects of variation in symptoms of bipolar disorder and depression at baseline.

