7.3. Description of Follow-up Assessment Data

Details on titration process, concomitant medications, pattern of service use, clinical events such as hospital re-admissions, emergency department admissions, suicide reattempts, psychometric measures, will be evaluated overall and by intervention group.

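### SAP Objective 4 targets depression symptoms, but it has no prespecified model for the PHQ-9 and reduces the ISS to a yes/no variable without a cut-off

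*SAP*

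**What the plan says.** **Objective.** SAP 5.1 keeps two symptom domains plus ideation in Objective 4: the effect of lithium "on symptoms of bipolar disorder and depression and suicidal ideation".

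**Endpoint.** SAP 5.2 states that "endpoint events for Secondary Objective #4 will be evaluated as a binary outcome". For the symptom part it adds: "Presence or absence of symptoms will be derived by the Internal State Scale". Suicidal ideation comes from the Columbia follow-up form. No threshold is given for the ISS.

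**Model.** SAP 5.3 specifies a generalised linear model, "namely Logistic regression, to model presence or absence of symptoms and suicidal ideation at each follow up visit", with random effects for baseline variation in bipolar and depression symptoms. The measure of baseline depression is not named.

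**Protocol.** Section VII, Secondary Data Analysis Plan, reads: "Secondary objective (d) will be evaluated using mixed effect models allowing for random variation in symptoms of bipolar disorder and depression at baseline". It mentions no dichotomy. In Table 1 the PHQ-9 is described as "Symptoms of depression" and the ISS as "Symptoms of bipolar disorder"; both have the study purpose of secondary outcome.

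**Collection.** Table 6 schedules both scales at baseline, T1, T4, the month 2 to 11 visits, early discontinuation, end of study and the 30-day visit. Table 7 continues both in participants who stop study drug but stay in active follow-up.

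**Descriptive reporting.** SAP 7.3 says that "psychometric measures, will be evaluated overall and by intervention group". It names no instrument.

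**The concern.** The objective has a depression half, and the protocol supplies a depression instrument measured repeatedly. The SAP assigns that instrument to no analysis. An analyst who follows the SAP literally will produce a between-arm estimate for a binary ISS state and for ideation, but none for the PHQ-9. The protocol's planned publication on managing symptoms of bipolar disorder and depression would then have no prespecified PHQ-9 model behind its depression part.

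Two further points follow. With no ISS cut-off stated, the threshold could be chosen after the data are seen. And cutting a multi-item score into yes/no usually discards information, so even the symptom analysis that is planned is weaker than the data allow.

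**Working it through.** **1. Objective against endpoint.**

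| Item | Protocol | SAP |
|---|---|---|
| Target | Bipolar and depression symptoms, ideation | Same (5.1) |
| Depression measure | PHQ-9, secondary outcome (Table 1) | Not named |
| Bipolar measure | ISS, secondary outcome (Table 1) | ISS, present/absent, no cut-off (5.2) |
| Model | Mixed effect models (VII) | Logistic with random effects (5.3) |
| PHQ-9 by arm | – | At most descriptive, instrument unnamed (7.3) |

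The mismatch is in the depression row. The model row is a smaller difference, because both documents use random effects.

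**2. Is there a stated figure to reproduce?** No. Neither document gives a sample size, power, SD, cut-off or prevalence for Objective 4. As context, the primary design figure does reproduce: HR = ln(1 − 0.0945)/ln(1 − 0.15) = 0.611, and a two-proportion test with 745 per arm, 15% against 9.45%, has 90.6% power at 5% and 90.3% at 4.8%, against the stated 90%. The primary analysis uses neither scale.

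**3. Information kept by a yes/no cut.** Assumptions: a normal score, a small mean shift, and a two-group comparison at one visit. If a share p is classed as having symptoms and c is the corresponding normal quantile,

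relative efficiency = φ(c)² / [p(1 − p)].

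- p = 0.50: φ(0)² / 0.25 = 2/π = 0.637.
- p = 0.20: φ(0.842) = 0.280, and 0.280² / 0.16 = 0.490.
- p = 0.10: φ(1.282) = 0.1755, and 0.1755² / 0.09 = 0.342.

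The documents do not give p, so a range of 10% to 50% is assumed. The subject equivalent is 1490 (evaluable sample, SAP 10) times the efficiency.

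| Share with symptoms | Efficiency | Loss | 1490 subjects are worth about |
|---|---|---|---|
| 50% | 0.637 | 36% | 949 |
| 40% | 0.622 | 38% | 927 |
| 30% | 0.576 | 42% | 858 |
| 20% | 0.490 | 51% | 730 |
| 10% | 0.342 | 66% | 510 |

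Under normality the even split is the best case.

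**4. What that means for power (illustration).** Take a standardised difference of 0.168, chosen so that the continuous score has 90% power with 745 per arm at two-sided 5%. The lithium share is then 1 − Φ(c + 0.168), where c is the normal quantile for the placebo share.

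| Placebo share | Lithium share | Power, binary |
|---|---|---|
| 50% | 43.3% | 73% |
| 30% | 24.4% | 68% |
| 20% | 15.6% | 60% |
| 10% | 7.4% | 44% |

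**5. Sensitivity to normality.** For a logistic-shaped score, the efficiency relative to comparing means is p(1 − p)π²/3: 0.82 at 50%, 0.69 at 30%, 0.53 at 20% and 0.30 at 10%. The corresponding losses are 18%, 31%, 47% and 70%. The 36% floor therefore belongs to the normal case only.

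**The case against.** The case on the other side has real substance.

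- **The PHQ-9 data are not lost.** They are collected throughout, including after drug discontinuation, and SAP 7.3 evaluates psychometric measures by arm. A reader might infer that the trial cannot report lithium's effect on depression symptoms. The documents do not support that. What is missing is a prespecified inferential analysis. SAP 7.1 adds t-tests and chi-square tests by arm, but presents them as checks of balance, and neither section names the PHQ-9 or gives a longitudinal effect estimate.
- **The SAP has not abandoned mixed modelling.** Section 5.3 keeps random effects and a hypothesis about change over time, and the protocol never promises continuous scores. This stands. The departure lies in the undefined dichotomy and the omitted scale.
- **A single loss figure cannot be derived.** A reader might infer that about a third of the trial's information goes. That figure is the median split of a normal score, and it applies to one secondary analysis. The planned model also uses repeated visits, so the formula is only a guide.
- **The Objective 5 mediator need not be the binary ISS.** A reader might infer that it inherits this variable. SAP 5.3 names no scale for the symptom mediator, so reuse is plausible but not stated.
- **The secondary-outcome label is loose.** Table 1 also gives it to the aggression and impulsivity trait questionnaires, which are collected only at baseline. The PHQ-9 differs: it is measured repeatedly and matches a named domain of the objective.
- **The ISS may capture depressive symptoms.** The documents cannot settle this. It is therefore not shown that participants with major depression have no depression outcome, only that the protocol's stated depression measure is unmodelled.
- **The objective is exploratory and not powered (SAP 5.1).** This limits the weight of the point. It does not explain omitting a listed outcome or leaving a threshold open.

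**Conclusion.** The point holds in a limited form. Objective 4 includes depression symptoms, yet its only symptom endpoint is a binary ISS variable without a cut-off, and the PHQ-9 has no prespecified between-arm model. This rests on reading the two documents together and needs no assumption.

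The size of the information loss does need assumptions. With a roughly normal ISS score it is at least 36%, and 36% to 66% for assumed symptom shares of 50% down to 10%; another score shape could give less or more. It concerns one exploratory analysis. The primary endpoint and its power are untouched. The point is worth correcting because the objective can be answered better from data already in hand, but it does not threaten the trial's main conclusion.

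**What to change.** In SAP 5.2 and 5.3:

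1. Name the PHQ-9 total as the depression-symptom endpoint and the continuous ISS scores as the bipolar-symptom endpoints. Analyse each with a linear mixed model containing treatment, visit, treatment-by-visit, baseline score and the stratification factors.
2. Keep the binary ISS variable as a supportive analysis, and state its cut-off before unblinding.
3. Keep the logistic model with random effects for suicidal ideation.
4. State which symptom score serves as the mediator in Objective 5.

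If the sponsor prefers to leave the PHQ-9 out of Objective 4, the SAP should say so and give the reason.

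The cost is one extra model per scale and a short SAP amendment. No new data, visits or participants are needed.

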5.3. Statistical Methods for Secondary Analyses

Secondary objective#1 will use a time to event, survival analysis to determine whether there is a treatment difference in event rates for each of the defined endpoints. The null hypothesis for each endpoint is that the two treatment groups do not differ in their hazard

rates. The alternative hypothesis is that the intervention group on lithium has a lower hazard rate than the placebo group. As with the primary analysis, log-rank test and Cox proportional hazards models will be used.

For secondary objective#2, the null hypothesis for each of the factors is that treatment effect does not differ over levels of the factor. The alternative hypothesis is that there is differential treatment effect over levels of the factor. Effect modification will be evaluated through regression methods. Cox proportional hazards regression model will include the treatment term, a term for the target factor, and the interaction term of the two. If the null hypothesis is rejected at $p=0.05$ level, i.e., the interaction term in the model is statistically significant, separate regression models will be refitted for each level of the factor. A forest plot will be used to display the results.

For secondary objective#3, the null hypothesis is that total event rates do not differ by treatment assignment, and the alternative hypothesis is that there is a difference in total event rates across treatment groups. We will use Generalize Linear Models (glm), namely Poisson regression, to model cumulative total of endpoint events with an offset for follow up time.

For secondary objective#4, the null hypothesis is that change in symptoms and suicidal ideation in the lithium group is similar to that of the placebo group. The alternative hypothesis is that there is a difference in change across treatment groups over time. We will use Generalize Linear Models (glm), namely Logistic regression, to model presence or absence of symptoms and suicidal ideation at each follow up visit, while allowing for random effects of variation in symptoms of bipolar disorder and depression at baseline.

Secondary objective#5 will be evaluated by Cox Proportional Hazard regression analysis method comparing regression coefficients for treatment effect in the models with and without the mediator (Sobel, 1982). Additionally, we will explore bootstrapping methods to evaluate mediators as described in MacKinnon et al.(2002), Preacher & Hayes (2008), and MacKinnon (2003).

6. Analysis Plan for Tertiary Objectives

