The mental health diagnosis used in this study will be based primarily on information from the structured diagnostic assessments conducted during the eligibility evaluation (See Section VI, Table 1 and Table 6). Any apparent discrepancies between these diagnoses and those in the medical record will be resolved by further inquiries to the patient (and, where appropriate, the family) about current and previous symptoms and further discussion with the patient’s mental health provider. The Research Team will establish a final diagnosis on the basis of the structured diagnostic assessments, the medical record, and other available data. Inclusion will require a Research Team diagnosis of bipolar disorder or current or recurrent major depression and the absence of exclusionary diagnoses together with the mental health provider’s concurrence with the validity of these diagnoses.

Procedures for the diagnosis of a current or recurrent Major Depressive Disorder are designed to identify lifetime diagnoses. For patients for whom the current attempt has occurred within the context of an initial episode of depression, admission will require that the criterion symptoms for a Major Depressive Episode are fully met, either at the time of the interview or when the episode was at its worst. For those with recurrent episodes, admission will require that the criterion symptoms were met at the times of screening, the baseline assessment, or when the current episode was at its worst.

Mental health comorbidities that are not exclusions include PTSD, panic disorder, generalized anxiety disorder, and personality disorders.

A potential concern about inclusion of individuals with personality disorder is that they may exhibit multiple, repeated episodes of suicide attempts or other forms of self-destructive behaviors, and that, in this context, attempts and self-destructive behavior may become less valid as surrogate measures for suicide. This possibility is addressed through the exclusion criterion related to multiple attempts (see below).

A medical record diagnosis of schizoaffective disorder may not be an exclusion when there is also documentation of bipolar disorder. As emphasized in DSM-5 (p. 138), “Schizophrenia, schizoaffective disorder, and delusional disorder are all characterized by periods of psychotic

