Both stratification and blocking will be utilized to control for potential imbalances in randomization. The randomization scheme will be stratified by participating site in addition to diagnosis (bipolar vs. depression) and history of prior attempts other than the index attempt (none vs. 1+ attempt). Stratification by site is necessary because of possible regional differences in clinical practices. Participants will be randomized to either lithium or placebo within permuted random blocks of 4 so that the treatment arms are balanced after every 4th randomization within the 4 strata at each site: bipolar with prior attempt, bipolar without prior attempt, depression with prior attempt, and depression without prior attempt. Breaking the blind at the end of each participant's time in the study is not expected to provide information about the treatment assignment of participants remaining in the study as block randomization is within multiple strata. Regardless, an extra treatment assignment will be inserted to each stratum of four to disrupt the blocks and make block size harder to discern.

A web-based randomization program validated by the MAVERIC CSPCC will be provided to study sites. At subject enrollment, Site Coordinators will enter the patient ID number, study site, and eligibility information into the randomization program to confirm that all eligibility criteria are met. If met, the program will select the first unused entry from the pre-specified list of random treatment assignments for the particular site. The lists will be stored on a secure server at MAVERIC CSPCC. In case the electronic system is down, the identical process can be followed manually and the randomization scheme telephoned or faxed to the site.

This CSP clinical trial is a double-blinded study in which neither the patient nor the site investigator knows to which of the two study arms the patient has been assigned. Emergency drug code envelopes will be prepared by the CSPCRPCC and shipped with the study drugs to the Pharmacy Service of the participating medical center prior to the study starting. Each envelope is numbered with a unique patient randomization number and contains the treatment assignment for

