 - 6. individuals with and without trait aggression
 - 7. subjects who have vs. have not received evidence based psychotherapies
- (c) To explore the effect of lithium augmentation of enhanced suicide prevention management on total occurrence of all event types combined and individual event type as follows:
 - 1. all suicide attempts
 - 2. all suicide attempts plus interrupted attempts
 - 3. all hospitalizations for the prevention of suicide
 - 4. all self-directed violence
 - 5. all emergency department visits
- (d) To explore longitudinally the effect of lithium augmentation of enhanced suicide prevention management on symptoms of bipolar disorder and depression and suicidal ideation
- (e) To explore mediators of the effect of lithium augmentation on prevention of episodes of suicidal self-directed violence, specifically improved control of symptoms and lithium plasma levels

Secondary objective (a) will use a time to event, survival analysis to determine whether there is a treatment difference in event rates for each of the defined endpoints. The null hypothesis for each endpoint is that the two treatment groups do not differ in their hazard rates. The alternative hypothesis is that the intervention group on lithium has a lower hazard rate than the placebo group. The log-rank test and Cox proportional hazards models will be used.

For secondary objective (b), the null hypothesis for each of the factors is that treatment effect does not differ over levels of the factor. The alternative hypothesis is that there is differential treatment effect over levels of the factor. Effect modification will be tested through the use of interaction terms in the Cox proportional hazards regression model with main effects of treatment and factor and an interaction of the two. A forest plot will be used to display the results.

Secondary objective (c) will be evaluated using Poisson regression to model for grand total numbers of events and for total number of each event type controlling for follow up time. The null hypothesis for this objective will be that total event rates do not differ by treatment assignment. The alternative hypothesis is that there is a difference in total event rates across treatment groups.

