As secondary objectives of the study, lithium efficacy will be evaluated for prevention of subtypes of suicidal self-directed violence, for all suicidal self-directed violence events (even after the first recurrence), for prevention of repeated events in subgroups as well as in the entire sample, and to identify potential mediators.

The tertiary objectives of the study are to extend the follow up period using electronically available data to describe patterns of lithium use following active participation in the study participants, as well as to evaluate rates and determinants of suicide reattempts and all cause mortality over a longer follow up period.

3. Investigational Plan

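### Total counts of repeat suicidal events and emergency visits are analysed by Poisson regression with no provision for overdispersion, so intervals will be too narrow if the counts are overdispersed, as is likely

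*SAP*

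**What the plan says.** SAP section 5.3 analyses objective 3 with a generalized linear model, "namely Poisson regression, to model cumulative total of endpoint events with an offset for follow up time". The Secondary Data Analysis Plan in Protocol section VII agrees: "Secondary objective (c) will be evaluated using Poisson regression to model for grand total numbers of events", and for totals of each event type, controlling for follow-up time.

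SAP section 5.2 defines the outcomes as a combined total of all episodes, and adds that "total counts of each component, in addition to all emergency department visits will be separate endpoints". SAP section 2 makes clear that events after the first recurrence count. Section 5.3 states a two-sided hypothesis for the objective: "the alternative hypothesis is that there is a difference in total event rates across treatment groups". It gives no significance level for it, although it gives 0.05 for the interactions in objective 2.

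SAP section 5.1 sets the status of all the secondary objectives: "Analyses for these objectives are exploratory in nature and as such, they are not statistically powered for formal hypothesis testing".

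No section supplies a scale parameter, a robust variance, a negative binomial model or a subject-level random effect for the counts. The frailty term in SAP section 4.4 is for site in the primary Cox model. The random effects in section 5.3 belong to objective 4.

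**The concern.** Poisson regression takes the variance of each person's count to equal its mean, given the covariates and follow-up time. The model as written names treatment and an offset only. If people differ in underlying risk, or one episode raises the chance of the next, the variance exceeds the mean. The rate ratio is still estimated sensibly, but its standard error is too small.

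The documents themselves treat repeat risk as uneven. Randomisation is stratified on whether there was any attempt before the index attempt (Protocol section VII, Randomization Plan). Of people with personality disorder, who may enrol, Protocol section V warns that "they may exhibit multiple, repeated episodes of suicide attempts or other forms of self-destructive behaviors".

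At stake are the intervals and p-values for the recurrent counts. Protocol section VI (Other Outcomes) wants attempt totals for comparison with other studies, and section XX plans a paper that draws on secondary aims c and d. These results are therefore likely to be read.

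**Working it through.** **The plan's own figures.** The documents give no mean count, dispersion, power or significance level for objective 3, so there is no figure to reproduce for it. The primary design, which supplies the sample size, does reproduce:
- hazard ratio = ln(1 − 0.0945)/ln(1 − 0.15) = 0.611
- events = 745 × (0.15 + 0.0945) = 182
- Schoenfeld power with 182 events at two-sided 0.048 = 91.1%, against 90% stated
- enrolment = 1490/0.8 = 1863, against 1862 stated.

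**Effect of overdispersion.** Let φ be variance/mean. The Poisson standard error is 1/√φ of the true one. A test at an assumed two-sided 5% then has actual type I error 2 × [1 − Φ(1.96/√φ)].

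| φ (assumed) | Poisson SE / true SE | Actual type I error |
|---|---|---|
| 1.0 | 1.00 | 5.0% |
| 1.25 | 0.89 | 8.0% |
| 1.5 | 0.82 | 11.0% |
| 2 | 0.71 | 16.6% |
| 3 | 0.58 | 25.8% |

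**Simulation check.** Gamma-Poisson counts under the null, 931 per arm, 40% leaving early at uniform times, log follow-up as offset, 6000 replicates per setting. With true Poisson counts, the plain model rejected in 4.8% to 4.9% of replicates. A sandwich variance gave 4.5% to 5.7% in every setting.

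For suicidal events, the simulated counts were calibrated so that 15% of people have any event in a year, the planned placebo rate. The average number of events per affected person was varied (assumed):

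| Events per affected person | Type I error, plain Poisson |
|---|---|
| 1.13 | 6.5% |
| 1.28 | 9.3% |
| 1.53 | 14.8% |
| 1.83 | 21.0% |

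For emergency visits the documents give no rate. Assumed means of 1 to 2 a year, with gamma variance of 0.5 to 4, gave 10% to 51%.

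**Rough anchor in the documents.** In the cited lithium-versus-valproate trial there were 18 attempts (Protocol section XII, Toxicity), and 6 + 8 = 14 of 98 patients had one (Protocol Table 2).
- Mean = 18/98 = 0.184.
- Extra attempts spread evenly (10 patients with one, 4 with two): sum of squares 10 + 16 = 26, variance = (26 − 98 × 0.184²)/97 = 0.234, φ = 1.27, type I error 8.2%.
- Extra attempts all in one patient (13 with one, 1 with five): sum of squares 13 + 25 = 38, variance 0.358, φ = 1.95, type I error 16.0%.
- Negative binomial fit to the mean and the 84 patients with none: φ = 1.41, type I error 9.8%.

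This anchor is weak. It is small, pools the arms and ignores unequal follow-up, and the protocol gives the period as 2 years in one place and 2.5 in another.

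**Suicide deaths.** A person contributes 0 or 1, so the variance is p(1 − p), which is below the mean p. Plain Poisson is slightly conservative there.

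**The case against.** The strongest reply is that the inflation is conditional. Nothing in the documents shows that these counts are overdispersed or by how much. That stands. A reader might infer that type I error is known to be well above 5%, and the documents do not support that.

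The larger values also sit poorly with the suicidal-event counts. Under a gamma-Poisson model with 15% having any event, the mean count is m = (φ − 1) × 0.1625/ln φ, where 0.1625 = −ln(0.85). At φ = 3 this gives m = 0.296, or 0.296/0.15 = 2.0 events per affected person in a year. The cited trial had 18/14 = 1.3 over a longer period. Excluding people with six or more lifetime attempts trims the tail further, although people with up to five remain.

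A reader might also infer that every count endpoint is affected. Suicide deaths are a counter-example.

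A third tempting reading is that the offset is invalid because the follow-up variable in the SAP code, FUdays, stops at the first event. The documents do not show this. FUdays is defined for the primary analysis in SAP section 4.3, while section 5.3 says only follow-up time. An offset ending at the first event would contradict an endpoint that counts later ones. At most the definition needs stating.

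Finally, the objective is exploratory and unpowered. That limits the consequence but does not remove the fault: lack of power explains wide intervals, not intervals that are too narrow. SAP section 1 allows documented deviations, so an analyst could correct the variance later, but then the choice would follow sight of the data.

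**Conclusion.** The point holds in conditional form. Both documents specify Poisson regression for recurrent counts and make no provision for overdispersion. Overdispersion is likely for repeat suicidal events and emergency visits. If it is present, a nominal two-sided 5% becomes about 8% at φ = 1.25, 11% at 1.5, 17% at 2 and 26% at 3. These ratios are assumptions, as is the 5% level. For attempts, the one anchor in the documents suggests roughly 8% to 16%. Emergency visits could be worse, but no rate is given.

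The effect is confined to the recurrent-count endpoints of exploratory objective 3. The primary log-rank test and the trial's main conclusion do not change.

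**What to change.** In SAP section 5.3, pre-specify one method for the recurrent counts: Poisson regression with a robust (sandwich) variance, or negative binomial regression. Make the choice before unblinding. The count of suicide deaths needs no change.

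As a clarification, define the offset as the log of time from randomisation to the earliest of 12 months, death or last contact, and state that it does not end at the first event.

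The cost is a short SAP edit, with no new data or patients. Intervals on the log rate-ratio scale widen by √φ: √1.25 = 1.12 (about 12%), √1.5 = 1.22 (22%) and √2 = 1.41 (41%). If the counts prove to be Poisson, almost nothing is lost: in those simulations the sandwich variance rejected in 4.6% to 5.0% of replicates.
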